# 18.7 APPENDIX 7: ELECTRONIC DIARY APPLICATION (SEE SAMPLES SCREEN SHOTS)

**47** | Page E L I R A - 1

How Full Are You?

### 18.8 APPENDIX 8: LIST OF POTENTIAL DRUG INTERACTIONS

	Weight positive medications (cause weight gain)	Weight negative medications (cause no gain* or weight loss)
DIABETES	Glipizide Glyburide Insulin Pioglitazone Rosiglitazone	Acarbose* Exanatide Glimepiride* Liraglutide Metformin Sitagliptan*
HYPERTENSION	Atenolol Clonidine Hydralazine Labetalol Prazosin Terazosin Valsartan	Amlodipine Captoprii* Carvedilo!* Enalaprii* Furosemide Hydrochlorathiazide* Lisinopril Losartan* Metoprolol* Olmesartan
PSYCHIATRIC	Citalopram Clozapine Lithium MAO-I Mirtazapine Olanzapine Paroxetine Phenothiazines Risperdone TCA	Amphetamines Buproprion Escitalopram* Fluoxetine Sertraline
CHRONIC PAIN	Amitriptyline Celecoxib Gabapentin Methadone Pregabalin	Acetaminophen* Baclofen* Carisoprodol* Cyclobenzaprine* Diclofenac* Fentanyl Hydromorphone Ibuprofen* Morphine Naproxen* Tramadol

FIGURE 1: Commonly prescribed weight positive, negative, and neutral\* medications.

\*List of drugs includes some pharmaceuticals that may impact study participation. May not be complete and is up to PI discretion.

### 18.9 APPENDIX 9: PATIENT PREFERENCE SURVEY

### **Elira Concept Test**

#### 8-10-17

- 1. Which of the following topics are you interested in?
  - a. Investing
  - b. Weight loss
  - c. Sports
  - d. Working out in the gym
  - e. Yoga
  - f. Martial Arts
  - g. Camping
  - h. Hunting / Fishing
  - i. Hiking / Bicycling
  - j. Cars / Motorcycles
  - k. Traveling
  - I. Fine dining
  - m. Home improvement
  - n. Fitness / Nutrition / Health
  - o. Movies / Entertainment
  - p. Politics / current events / news
  - q. Books
  - r. Shopping
  - s. None of the above
- 2. Are you interested in losing weight?
  - a. Yes
  - b. No
- 3. Please select your gender.
  - a. Male
  - b. Female
  - c. Prefer not to respond
- 4. Please select your age.
  - a. Under 18
  - $\begin{array}{lll} b. & 18-24 \\ c. & 25-34 \end{array}$

  - d. 35 44
  - e. 45 54
  - f. 55 64
  - q. 65 74
  - h. 75 or older
- 5. How much weight do you think you need to lose?
  - a. None
  - b. Less than 5 lbs
  - c. 5 10 lbs
  - d. 11 15 lbs
  - e. 16 20 lbs
  - f. More than 20 lbs

- g. Not sure
- 6. Please enter your height in feet and inches.
- 7. Please enter your weight in lbs.
- 8. A number of weight loss programs offer the potential to lose 1-2 lbs per week. Do you consider this a reasonable amount of weight for you to lose per week in a weight loss program?
  - a. Yes
  - b. No, I would expect to lose less per week
  - c. No, I would expect to lose more per week
- 9. Which, if any, of the following have you attempted in order to lose weight in the past? Select all that apply.
  - a. Dieting on your own (not through a specific program)
  - b. Dieting with online coaching or support (like MyFitnessPal)
  - c. Exercise or increasing amount of exercise
  - d. Commercial weight loss program (Jenny Craig / Weight Watchers, etc.)
  - e. Gym membership
  - f. Medical weight loss through a physician
  - g. Behavioral modification therapy
  - h. Prescription diet pills or other prescription medications
  - i. Surgical or other invasive procedures
  - j. Body sculpting targeting specific areas, like Cool Sculpting or liposuction
  - k. Other (please specify)
  - I. I haven't tried to lose weight in the past
- **10.** Please rate your level of success, if any, with past weight loss attempts.

	Very successful	Moderately successful	Slightly successful	Not at all successful	I didn't give it a chance
Dieting on your own (not through a specific program)	a.	b.	C.	d.	e.
Dieting with online coaching or support (like MyFitnessPal)	a.	b.	C.	d.	e.
Exercise or increasing amount of exercise	f.	g.	h.	i.	j.
Commercial weight loss program (Jenny Craig / Weight Watchers, etc.)	a.	b.	C.	d.	e.
Gym membership	a.	b.	C.	d.	e.
Medical weight loss through a physician	a.	b.	C.	d.	e.
Behavioral modification therapy	a.	b.	C.	d.	e.
Prescription diet pills or other prescription medications	a.	b.	C.	d.	e.
Surgical or other invasive procedures	a.	b.	C.	d.	е.

specific	ulpting targeting areas, like Cool g or liposuction	a.	b.	C.	d.	e.
Other		а	h	C	Ь	е .

- 11. Which of the following medical aesthetics or cosmetic procedures, if any, would you consider? Select all that apply.
  - a. Plastic surgery (e.g., face lift, tummy tuck, etc.)
  - b. Laser dermal treatments
  - c. Injectibles like Botox
  - d. Dermal fillers like Restylane and Juvederm
  - e. Targeted body sculpting or fat elimination like liposuction or Cool Sculpting
  - f. Would not consider any of the above
- 12. What is the primary reason you want to lose weight?
  - a. Health-related reasons
  - b. Lifestyle reasons (want to be able to be more active, etc.)
  - c. Recommended by my Company's wellness program
  - d. Special event (wedding, reunion, party, etc.)
  - e. Just want to look better
  - f. Other (please specify)
- 13. What other reason(s), if any, do you have for wanting to lose weight? Select all that apply.
  - a. Health-related reasons
  - b. Lifestyle reasons (want to be able to be more active, etc.)
  - c. Recommended by my Company's wellness program
  - d. Special event (wedding, reunion, party, etc.)
  - e. Just want to look better
  - f. Other (please specify)
  - g. No other reason
- 14. Is it easy or difficult for you to lose weight?
  - a. Very easy
  - b. Somewhat easy
  - c. Sometimes easy, sometimes difficult
  - d. Somewhat difficult
  - e. Very difficult
  - f. I've never tried to lose weight before
- 15. What are your primary barriers to weight loss? Select all that apply.
  - a. Time
  - b. Cost
  - c. Willpower
  - d. Appetite control
  - e. Fear of failure
  - f. Concerns about side effects of medication or surgery
  - g. Other (please specify)
- 16. Please rank your weight loss goals in order of importance. "1" should be the most important.
  - a. Achieve a healthy metabolism
  - b. Control my appetite
  - c. Lose weight
  - d. Achieve a healthy diet

- e. Increase fitness
- f. Normalize my body mass index (Achieve a BMI of less than 25)
- g. Improve my body shape
- h. Become leaner
- i. Improve my looks

Please evaluate the following concept closely and answer the questions that follow.

An Introduction to Elira

#### **Concept Statement**

Elira represents an entirely new way to lose weight by controlling appetite. Simply put, eating too much typically results in excess weight, and the right way to improve health is to lose that weight. The Elira electronic skin patch helps make weight loss easier by providing a means to suppress appetite by causing a feeling of fullness (or satiety). This in turn allows you to "reset" your caloric intake and better control hunger pangs and the urge to snack excessively. Think of Elira as a personal dietary assistant that is typically worn during daylight hours for a 12-week course of treatment.

Elira is intended to be a FDA-approved, wearable, electronic skin patch that is easy to use and non-invasive (see picture above). It is controlled by a smartphone and delivers electrical stimulation to specific sensory nerves in your abdomen which results in a feeling of fullness, making it easier to maintain a weight loss diet. The Elira device is intended to be worn during waking hours and it is programmed to deliver stimulation sessions (typically 3 per day) around mealtimes. The user does not have to do anything to activate the therapy – it is all done automatically.

Elira treatments are not painful – when activated, users feel a tingling sensation to the skin. No significant side effects have been observed. What makes Elira unique are its medical and scientific credentials based on clinical trials, coupled with the ease of use of a smartphone-controlled, unobtrusive skin patch.

Other FDA approved medical devices for weight loss typically require surgical implantation with all of the risks and side effects associated with an invasive procedure. Also, implanted devices tend to be very expensive with costs ranging in the thousands of dollars – costs that are often not covered by insurance. Elira is intended to be an entirely non-invasive, FDA-approved medical device for weight loss and appetite control without any of the risks and costs associated with surgical implantation. It is designed to be affordable and extremely safe, allowing users a chance to avoid the downsides of either surgery or drugs, and is expected to result in greater weight loss than diet & exercise alone.

- 17. Which best describes how you feel about buying Elira, assuming it fits your budget?
  - a. Definitely would buy
  - b. Probably would buy
  - c. Might or might not buy
  - d. Probably would not buy
  - e. Definitely would not buy
- 18. Which best describes how much you think you would like or dislike the Elira device?
  - a. Very appealing
  - b. Somewhat appealing
  - c. Neither appealing nor unappealing
  - d. Somewhat unappealing
  - e. Very unappealing
- 19. What, if anything, do you like MOST about this product?
- 20. What, if anything, concerns you or do you dislike about this product?
- 21. How believable do you find this Elira device to be after reading the statement above and assuming that Elira is approved by the FDA as a medical device for weight loss?
  - a. Very believable
  - b. Somewhat believable
  - c. Neither believable nor unbelievable
  - d. Somewhat unbelievable
  - e. Very unbelievable
- 22. How willing would you be to wear the Elira device daily for 3 months if it resulted in your achieving your weight loss objectives?
  - a. Very willing
  - b. Moderately willing
  - c. Slightly willing
  - d. Not at all willing
- 23. Which of the following physicians would you be most likely to visit in order to obtain the Elira device?
  - a. General/Family Practitioner
  - b. OB/GYN
  - c. Cosmetic Surgeon
  - d. Medical Weight Loss Clinic or Spa
  - e. Cosmetic Dermatologist
  - f. Therapist
  - g. Other (please specify)

24. How would you rate this product in terms of being new and different from other weight loss products that you are familiar with?

- a. Very unique
- b. Somewhat unique
- c. Not at all unique
- 25. How would you improve the device?
- 26. The following are three medical weight loss treatments that have been shown to be effective, but which have certain patient eligibility requirements:
  - a. Bariatric surgery permanently reducing the size of the stomach or placing a band around it
  - b. Endogastric implants a procedure using an endoscope to place a balloon in the stomach
  - c. Prescription weight loss drugs

For each of these treatments, how likely would you be to talk to your health care provider about your eligibility for the treatment, and about the costs and side effects associated with it?

	Highly likely	Somewhat likely	Not sure	Somewhat unlikely	Not at all likely	Already looked into it
Bariatric surgery	a.	b.	C.	d.	e.	f.
Endogastric implants	a.	b.	C.	d.	e.	f.
Prescription weight loss drugs	a.	b.	C.	d.	e.	f.

- 27. Diet and exercise have been shown to be effective ways to lose weight or control one's weight. However, success depends on one's ability to adhere to a dietary or exercise plan. If Elira is able to make it easier for you to control your appetite and lose more weight than through diet and exercise alone, would you consider purchasing an Elira device, assuming it fits your budget?
  - a. Highly likely
  - b. Somewhat likely
  - c. Not sure
  - d. Somewhat unlikely
  - e. Not at all likely

If your answer is No, then what would make Elira attractive enough for you to purchase it? (Open Ended)

- 28. Assuming Elira fits your budget, if using Elira helped you lose 15% more weight than you would have lost by diet and exercise alone, how likely would you be to want to try it?
  - a. Highly likely
  - b. Somewhat likely
  - c. Not sure
  - d. Somewhat unlikely
  - e. Not at all likely

28. How likely would you be to consider using an Elira device if it was shown to be safe and effective in helping you achieve your weight loss goals, but was not covered by insurance provided it cost no more than \$25/month over a 12-month period?

- a. Highly likely
- b. Somewhat likely
- c. Not sure
- d. Somewhat unlikely
- e. Not at all likely
- 29. How likely would you be to consider using an Elira device if it was shown to be safe and effective in helping you achieve your weight loss goals, but was not covered by insurance provided it cost no more than \$50/month over a 12-month period?
  - a. Highly likely
  - b. Somewhat likely
  - c. Not sure
  - d. Somewhat unlikely
  - e. Not at all likely
- 30. How likely would you be to consider using an Elira device if it was shown to be safe and effective in helping you achieve your weight loss goals, but was not covered by insurance provided it cost no more than **\$100/month** over a 12-month period?
  - a. Highly likely
  - b. Somewhat likely
  - c. Not sure
  - d. Somewhat unlikely
  - e. Not at all likely
- 31. Following is a list of features that we hope to incorporate into our Elira device in the future. Please evaluate each and rank based on importance. "1" should be the most important and "5" should be least important.
  - a. Rescue sessions (i.e., the ability to schedule additional Elira treatments in-between mealtimes in order to curb the need to snack.)
  - b. Ability to connect with other devices like Fitbit so as to integrate exercise information
  - c. Ability to connect with social networks so that you aren't alone while dieting to lose weight
  - d. Ability to connect with dietary apps like MyFitnessPal or other online weight loss programs so as to integrate online dietary advice, calorie counting programs, healthy recipes, etc.
  - e. Access to live dietary coaching and support
  - f. Ability to directly order healthy foods for home delivery
- 32. Do you consider yourself to be one of the following? Select all that apply.
  - a. Vegetarian
  - b. Vegan
  - c. Organic Foodie
  - d. Low-carb Dieter (such as Paleo)
  - e. None of the above
- 33. What was the highest level of education you have completed?
  - a. Less than high school graduate
  - b. High school graduate
  - c. Trade school
  - d. Some college
  - e. Graduated college
  - f. Post graduate work
  - g. Prefer not to answer

- 34. Which one of the following best describes your marital status?
  - a. Married
  - b. Single
  - c. Divorced
  - d. Separated
  - e. Other
  - f. Prefer not to answer
- 35. Which one of the following best describes your current employment status?
  - a. Employed full time
  - b. Employed part time
  - c. Full-time mother
  - d. Student
  - e. Not employed
  - f. Other
  - g. Prefer not to answer
- 36. Which one of the following best describes your ethnic background?
  - a. Caucasian (not Hispanic or Latino)
  - b. Hispanic or Latino
  - c. African American
  - d. Asian or Pacific Islander
  - e. Other
  - f. Prefer not to answer
- 37. Which one of the following groups contains your total annual household income before taxes?
  - a. Under \$30,000
  - b. \$30,000 \$49,999
  - c. \$50,000 \$74,999
  - d. \$75,000 \$99,999
  - e. \$100,000 \$124,999
  - f. \$125,000 \$149,999
  - g. \$150,000 or more
  - h. Prefer not to answer

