#### Visit Schedule

Screening/Baseline Visit 0 (-1 week; ± 7 days) – Obtain Informed Consent prior to any study procedures. Confirm subject has met all inclusion criteria and no exclusion criteria. History & Physical including height & weight, diet history, baseline clinical parameters, provide laboratory requisition, urine pregnancy test for women of childbearing potential (WOCBP), and questionnaires. Initiate subject weekly paper diary with training for weekly completion. Subjects will be instructed to return with their weekly paper diary(ies) at their next scheduled visit.

**Enrollment/Randomization Visit 1 (Day 0; ± 7 days)** – Confirm subject continues to meet all inclusion criteria and no exclusion criteria. Assessment of T6/T7 dermatomes, clinical parameters, BP, weight, perform urine pregnancy test for WOCBP if not done at screening, administer TFEQ-R18V2 Questionnaire, assess for adverse events and changes to concomitant medications. Subjects will be randomized based on the blocked randomization algorithm.

Treatment and Control subjects will be instructed to follow a healthy 1200 calorie diet throughout the study, an electronic scale with instructions on use will be provided, and a paper diary with training for weekly completion will be provided. Subjects will be instructed to return with their paper diary(ies) at the next scheduled visit.

Only the treatment subjects will receive a handheld smartphone with the custom application and an Elira wearable patch system. It is recommended for treatment subjects to utilize an TENS Clean-Cote Skin Wipes and/or alcohol prep pad to maintain a clean application area for the treatment. Treatment subjects will also receive Cetaphil Moisturizing Lotion to be used if any irritation occurs at the treatment site. Subject will

be instructed to notify site immediately if any irritation occurs. Treatment subjects will stimulate under the supervision of the investigator or coordinator for 30 minutes prior to being discharged with the device. Treatment subjects will be assessed for toleration of the stimulation to further evaluate dose adjustment. Treatment subjects will be discharged with the Elira wearable patch system & Smartphone App and instructions on use. Treatment subjects will be instructed to return with the Elira wearable patch system and smartphone app at their next scheduled visit.

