#### 5.3 ASSIGNMENT & BLINDING

Subjects meeting the Inclusion and Exclusion criteria will be enrolled and randomized into either Treatment or Control groups. The randomization algorithm will be blocked to account for site bias and to ensure counterbalance across sites. As this is an open label study, there will be no consideration for blinding.

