#### 9.8 QUESTIONNAIRES

All subjects will be required to complete the Patient Preference Survey and PHQ-9 at screening/baseline visit. All subjects will be required to complete a weekly VAS diary for hunger and appetite from screening/baseline until completion of the study. All subjects will be required to complete the TFEQ-R18V2 at enrollment and at each Therapy Visit (Appendix 3). All subjects will be required to complete PHQ-9, TFEQ-R18V2, and Patient Preference Survey at the last study visit (Visit 5 or early termination visit).

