#### 10.1 RISKS

#### 10.1.1 Application and post application risks

While the TENS unit utilized in the present study delivers therapy in a comparable manner to standard commercially available TENS units, there are some risks associated with the device. These include skin irritation at the site of electrode application, numbness and tingling, pain and burning sensations at the site of stimulation. In addition, there is some chance that subjects may feel some gastrointestinal (GI) symptoms including nausea or other GI discomfort (heartburn, dyspepsia, cramping). Dropping the unit may cause damage to the TENS unit. Subjects are instructed to avoid use of the device if it has been damaged in any way and not to use the device while it or any portion of the subject are immersed in water. Subjects are instructed to contact PI or designee, if therapeutic sensation is not present. Any discomfort associated with TENS should be immediately reported to the PI or designee.

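### Before randomisation, every subject reads that the device should outperform diet and exercise and does not hurt, which adds avoidable expectation bias to an open-label trial with no sham

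*Combined protocol and SAP*

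**What the plan says.** Section 9.8 sets the timing: "All subjects will be required to complete the Patient Preference Survey and PHQ-9 at screening/baseline visit". Section 9, section 9.2 and the Visit 0 column of Appendix 6 agree. Randomisation comes one visit later; the Visit Schedule says under Visit 1 that "Subjects will be randomized based on the blocked randomization algorithm".

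Midway through the survey (Appendix 9) subjects are told: "Please evaluate the following concept closely and answer the questions that follow". The concept statement that follows says the device "is expected to result in greater weight loss than diet & exercise alone". It also says that nerve stimulation makes the user feel full, that "Elira treatments are not painful", that "No significant side effects have been observed", and that the device is designed to be very safe.

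The protocol's own risk text, section 10.1.1, lists "skin irritation at the site of electrode application, numbness and tingling, pain and burning sensations at the site of stimulation".

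On masking, section 5.3 says: "As this is an open label study, there will be no consideration for blinding". Under section 5 the control group gets the diet, the paper diary and the scale, but neither the patch nor the app. There is no sham.

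**The concern.** The efficacy sentence states the hypothesis under test: device plus diet against diet alone. Every subject is asked to study it and then learns, without masking, which arm they are in. Treated subjects have been told to expect fullness, little discomfort and more weight loss. Control subjects have been told that something they will not receive is expected to work better.

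This could lead treated subjects to rate their appetite lower and mention fewer device effects, and lead controls to put in less effort or leave early. Each of these would make the device look better. No section withholds the statement until after allocation, measures expectation, or plans an analysis of it. Analysis cannot remove the effect once subjects have read the text.

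**Working it through.** The plan gives no figure on this point, so the main check is to set the passages side by side.

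**1. Exposure.** The survey is at Visit 0 for all subjects and randomisation is at Visit 1. Exposure is therefore universal and precedes allocation.

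**2. What each assertion can reach.**

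| Assertion in the concept statement | Outcome it bears on | How that outcome is obtained |
|---|---|---|
| Stimulation produces fullness | Appetite score, secondary (6.1.3) | Subject-reported (6.2) |
| Appeal and benefits of the device generally | Preference score, ancillary (6.1.4) | Subject-reported, on this same survey |
| Not painful, no significant side effects, very safe | Adverse device effects (8.1.1) | Partly subject report (section 11), plus staff assessment and dermatome examination at visits |
| More weight loss than diet and exercise | %TBWL, primary (6.1.2) | Weight obtained at all six visits (Appendix 6) |

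The first two outcomes are directly exposed, the third partly. The fourth can move only through behaviour: how hard subjects diet and whether they stay. Section 2.1 itself accepts that psychosocial factors can affect appetite and weight loss.

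**3. Where a difference between arms arises.** Both arms read the same text, so the text alone creates no difference. The difference comes when subjects learn their arm, with no sham to hold expectation equal. The open-label design would carry some expectation bias without the survey; the statement adds to it.

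**4. Consistency with the risk text.** The flat statement that treatment is not painful cannot stand beside pain and burning in section 10.1.1. Section 9.12.1 also describes a mild tingling or burning sensation as typical. The sentence on side effects is a different matter: it reports what has been seen so far, while section 10.1.1 lists what might occur.

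**5. Illustration of sensitivity, with the bias assumed.** From section 8.2: SD 5 points of %TBWL, 75 per group, 30% dropout, so 75 × 0.70 = 52.5, taken as 52 completers per arm. No alpha is stated for the primary test; two-sided 0.05 is assumed from the 95% two-sided intervals in section 8. Suppose the device has no true effect and expectation shifts the arm difference by *b* points:

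SE = 5 × √(2/n), which is 0.981 for n = 52 and 0.816 for n = 75.

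Chance of a significant result favouring the device = Φ(b/SE − 1.96).

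| Assumed shift *b* | n = 52 per arm | n = 75 per arm |
|---|---|---|
| 0 | 2.5% | 2.5% |
| 0.5 | 7% | 9% |
| 1.0 | 17% | 23% |
| 1.5 | 33% | 45% |
| 2.0 | 53% | 69% |

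For scale, the planned difference is 7.5 − 3.5 = 4.0 points. Here *b* is the whole expectation effect from all sources; the documents do not allow the statement's share to be separated out.

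**The case against.** **The primary endpoint is measured.** A reader might infer that the main result is self-reported. It is not: weight is taken at visits, and blood pressure, lipids, ALT, HbA1c and BMI are measured too. This stands, and it limits the point mainly to appetite, preference and part of adverse event ascertainment.

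**The direction is not fixed.** A reader might infer that everything pushes towards the device. The documents do not show that. Controls told of a better option might try harder. Treated subjects promised painless treatment who then feel burning might report more, or stop. If discouraged controls with poor weight loss leave, last value carried forward (section 8.3) would often hold them at a small loss and widen the difference, though this depends on when they leave. The completer analysis (section 8.4) would drop them and could narrow it. This stands; favouring the device is plausible, not certain.

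**Controls are not told they received the inferior option.** The text precedes allocation and speaks of what is intended and expected. Baseline TFEQ is taken at Visit 1, after exposure, so priming common to both arms is already in that baseline. This stands, but it does not remove the effect of learning one's arm afterwards.

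**Safety is well protected.** The Protocol Summary and section 6.1.1 rest the primary safety endpoint on serious events, which a survey sentence is unlikely to suppress. Section 2.1 promises disclosure of all potential side effects before enrolment, and consent comes first at Visit 0. This stands in part. Section 8.1.1 brings adverse device effects into the primary safety definition, and the comparator is historical, so no concurrent arm would offset under-reporting. The consent wording is not in the public documents and cannot be weighed.

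**The side-effect sentence contradicts the risk list.** A reader might infer this too. An absence of significant effects so far is compatible with a list of possible risks expected at low frequency (section 10.1.2). Only the wording on pain is a clear conflict.

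**Conclusion.** The concern holds in limited form. Every subject reads an assertion of the trial's hypothesis before randomisation, in an open-label trial with no sham and no provision for expectation. This adds an avoidable bias that plausibly favours the device. It is most direct for self-reported appetite, preference scores and subject-reported adverse device effects, and only indirect for %TBWL, through diet effort or differential dropout.

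Its size cannot be derived from the documents. The table above shows only how sensitive the primary comparison would be to an assumed shift; it does not estimate this statement's effect. The open-label design would leave some expectation bias even with a neutral survey.

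Separately, and whatever view is taken on bias, the survey's claim of painless treatment and the pain and burning in section 10.1.1 must be reconciled. The change is worth making because it is cheap and reaches every subject, not because a large distortion has been shown.

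**What to change.** Replace the concept statement in Appendix 9 with a neutral device description, used word for word at Visit 0 and Visit 5. It should say what the patch is, how it is worn and controlled, and that its effect on weight and appetite is under study. Remove five assertions: superiority over diet and exercise, the production of fullness, painlessness, the absence of significant side effects, and the claim of very high safety. Check that what remains agrees with section 10.1.1.

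The cost is one form edit, with ethics approval of the change. The baseline-to-end preference comparison in section 6.1.4 is kept. The sponsor loses baseline reaction to its intended marketing text; this can still be collected at Visit 5, after the final weight, TFEQ and adverse event assessments.

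Moving questions 17 to 31 as a block to Visit 5 is less attractive. It removes the baseline for the preference endpoint and takes in question 26, which concerns surgery, implants and drugs, not this device.
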